	Median time to result standard of care	Median time to result Truenat	Alpha	Power	Sample size per arm	
	3 (sd = 14)	1 (sd = 14)	0.05	0.8	29	
	3 (sd = 21)	1 (sd = 21)	0.05	0.8	34	
	3 (sd = 14)	2 (sd = 14)	0.05	0.8	175	
	3 (sd = 21)	2 (sd = 21)	0.05	0.8	211	
Eligibility criteria for	Inclusion Crite	eria:				
randomised comparison	 Peop Slema Able as par Exclusion cri Cann Curre Patier Patier 	 clusion Criteria: People aged 12 years old or above presenting to mobile CXR based screening in Sleman district and Yogyakarta City Able and willing to consent. For adolescents aged 12-17, verbal consent as well as parental/guardian informed consent will be required Exclusion criteria: Cannot provide sputum Currently receiving anti-TB therapy Patients who are seriously ill and need to be admitted to hospital Patients with potential COVID-19 referred for further assessment 				
Eligibility Criteria	1. Post-	Training Assess	sment (Object	tive 1a): All lab	ooratory staff and h	ealth care
operational feasibility and	work	ers trained in po	errormance of	ruenat assay	s who consent to p	barticipate
acceptability assessments	2. Feasi mobi	bility and HCW le screening ser	acceptability	(Objective 1c) sent to particir	: All HCW involve pate.	d in the
	3 Scree	ning particinan	t accentability	(Objective 1d). Adults 18 years of	of age or older
	who	screened positiv	ve for presum	ptive TB in the	e active case finding	g program
	within	n the preceding	1 week and p	provide inform	ed consent; and pa	rents and

	legal guardians who have a child aged 12 to 17 years that screened positive for presumptive TB in the active case finding program within the preceding 1 week and provide informed consent.		
Study Timeline	Ethics Clearance	Q3 2022	
	Importation	Q3 2022	
	Training + post training Assessment	Q4 2022	
	Participant enrolment	Q4 2022–Q2 2023	
	Data Cleaning + analysis	Q3 2023	
	Total duration 12 months		

2 Study Schedule of Events

Procedure	Day 1	Day 1-3	Day 7-21
Informed consent	×		
Eligibility assessment	x		
Enrolment	x		
Contact information	x		
Medical history + screening assessment	x		
TB diagnosis assessment	x		x
Referral to health facility for treatment based on Truenat MTB		x	
Plus and MTB-RIF Dx result			
Collection of data from health facilities and laboratory			x
Interview with selected participants for user acceptability			x

3 Introduction

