4.2 Secondary objectives

- 2. Comparison of decentralised Truenat to centralised Xpert testing within community mobile TB case finding service for median time to result for those tested
- 3. Comparison of decentralised Truenat versus centralised Xpert testing for median time to commence treatment for bacteriologically confirmed TB cases

5 Methodology

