Participants attending the TB active case finding service who screen positive for potential TB by symptoms or chest X-ray will be invited to participate in the study. A study team member will explain the participant information and consent form (PICF) in person and participants who consent to participate will sign and date the PICF. For participants who are illiterate, thumbprint, witness signature and date will be recorded on the PICF. Persons who do not consent to participate in the study will receive standard of care diagnosis (submit a single sputum specimen for central GeneXpert laboratory testing) and their results will not be included in the study. Potential participants have the time between the initial invitation to participate and the cessation of TB screening by the mobile active case finding service on that day to decide whether they wish to participate.

Data on study enrolment will be entered into a study-specific enrolment instrument in the ZTB YY active case finding REDCap database. The instrument will record the person's patient ID as well as their study ID and the details of their consent.

A nurse will discuss with the participant the potential that they have TB and that they require further testing for TB. They will have the process for sputum sample collection explained and spot sputum samples will be collected under observation following a standard approach for ensuring good quality sputum collection and infection control. Depending on the diagnostic

LOCATE TB Research Protocol v1.1 (2022-08-25)

strategy assigned for the particular screening day the participant will receive either standard of care or decentralised Truenat testing:

- For standard of care participant samples will be sent to a centralised laboratory for GeneXpert testing. The participant will be informed that they will be notified of their results when they become available in 1-3 days. Those with GeneXpert MTB positive results will be informed by telephone to attend the nearest puskesmas for counselling and commencement of TB treatment. Those testing GeneXpert negative for MTB will have their case reviewed by the doctor at the health facility for their catchment to determine if they need further follow up or not in accordance with the standard ACF protocols.

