- For decentralised **Truenat**, two spot sputum samples will be collected and the participant will be informed that their sample will be tested on the day, and will be asked if they prefer to wait for the result or be contacted when the result is available.
 - Where a patient has a positive result on Truenat MTB Plus, the Truenat MTB-RIF Dx assay will be performed to test for rifampicin resistance. Patients with a positive result on Truenat MTB Plus will be informed of the result and advised to attend the nearest puskesmas or hospital for counselling and commencement of TB treatment, or referral to another facility of their choice for treatment.
 - Those testing negative for MTB will have their case reviewed by a doctor at the catchment health facility to determine if they need further follow up in accordance with the standard ACF protocols; and taking into consideration the result of the GeneXpert MTB/RIF assay
 - Due to National Tuberculosis Program requirements all patients tested with Truenat will also be tested with GeneXpert MTB/RIF using the second spot sputum sample. Treatment will be initiated based on positive Truenat or GeneXpert Mtb/RIF result, with review by the TB active case finding service doctor of cases where the result is discordant.
 - Commencement of TB treatment will be according to standard national TB protocols. Further clinical care and diagnostic investigations will be provided within governmental health care services. If a patient wishes to seek further care at a specific health facility or service of their choosing they will be provided with a referral.

The testing and treatment algorithm for patients in the Truenat Arm

Follow-Up Interview

Participants will be called at a 14-day phone visit (+/- 7 days). Three attempts will be made to contact a participant by phone. In the event that the participant is still not contacted, a phone call to the agreed trusted contact will be made to find out about the participant's whereabouts and to ask if they can arrange for the participant to return a call or to be visited at an acceptable time. A home visit will be conducted for those participants who cannot be reached by phone or who identify that they prefer a home visit or do not have access to a phone.

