5.7 Outcome Measures

Primary Endpoint

- 1. The operational feasibility of point-of-care Truenat, which will be assessed by:
 - a. Adequacy of Truenat training as measured by post-training assessment
 - b. Operational performance of Truenat as measured by platform failure rates and error rates
 - c. Instrument User and health service provider views regarding feasibility and acceptability of Truenat.
 - d. Screening participant views regarding acceptability of point-of-care Truenat performed within mobile active TB case finding service

Secondary endpoints

- Median time from sample collection to result for Truenat compared to centralised GeneXpert Mtb/RIF
- The median time from sample collection to treatment initiation for Truenat compared to centralised GeneXpert Mtb/RIF

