For study participants who are tested using a TB molecular diagnostic test, the median time from sample collection to result will be calculated and a test of significance will be performed on the medians from the standard of care group and the Truenat group. The expected number of patients diagnosed with bacteriologically confirmed TB is expected to be too small to give sufficient power to detect a difference in median time to treatment start in these patients. Nonetheless, the median time from sample collection to treatment initiation will be calculated for the two groups. Time to event analyses will be described by Kaplan-Meier-curves by diagnostic arm. Details will be presented in the Statistical Analysis Plan.

Interquartile ranges (IQRs) and box and whisker plots will be generated for all medians, with differences in medians compared using the Wilcoxon signed rank test (Mann-Whitney *U*). Interim data analysis will occur at the study mid-point, with results reviewed by the study team.

Endpoint	Numerator	Denominator	Data source
Objective 1	 		 
Proportion of	Staff trained	All staff trained	Post training assessment
staff trained who	achieving		
were deemed	proficiency in post		
proficient	training assessment		
Proportion of	Number of Truenat	Number of	Mobile ACF service error
tests performed	tests with error or	Truenat tests	form
with an error	invalid result	performed	
Proportion of	Time (hours and	Time (hours and	Mobile ACF service
time of device	minutes) of device	minutes) during	laboratory availability
unavailability for	unavailability during	screening days	records
use during	Truenat screening	when Truenat	

TABLE 1: ENDPOINTS AND DATA SOURCES

working day	days for any reason	randomized to be	
		available	
Objectives 2 and 3			
Madian tinga ta		Γ	Activo caso finding
Median time to			Active case midning
diagnostic test result			database (Redcap)
for participants			Laboratory database
tested with a TB			
molecular diagnostic			
test			
Median time to			Active case finding
treatment			database
initiation for			Deeleenee Deteleen
participants with			Pusksemas Database
an initial positive			Week-1 telephone call
result on a TB			
molecular			
diagnostic test			

Mixed-Methods Analysis and Outputs

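### Section 5.4.2 words the referral of positives differently by arm, a small and avoidable difference inside the secondary time-to-treatment comparison

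*Protocol*

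**What the plan says.** The Baseline Visit text in protocol section 5.4.2 describes the two arms in separate bullets.

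- Standard of care: "Those with GeneXpert MTB positive results will be informed by telephone to attend the nearest puskesmas for counselling and commencement of TB treatment".
- Truenat: positives are told their result and "advised to attend the nearest puskesmas or hospital for counselling and commencement of TB treatment, or referral to another facility of their choice".

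The last item under the Truenat bullet says that treatment follows national TB protocols and that further care takes place in government services. It then adds a sentence beginning "If a patient wishes to seek further care at a specific health facility or service of their choosing", under which the patient gets a referral. That sentence names no arm.

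Objective 3 in section 4.2 is "Comparison of decentralised Truenat versus centralised Xpert testing for median time to commence treatment for bacteriologically confirmed TB cases". The matching endpoint in section 5.7 is "The median time from sample collection to treatment initiation for Truenat compared to centralised GeneXpert Mtb/RIF". Section 5.10.2 plans medians by group, Kaplan-Meier curves by arm and a rank test for differences in medians. It also warns that the number of confirmed cases is expected to be "too small to give sufficient power to detect a difference in median time to treatment start in these patients".

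**The concern.** A randomised comparison of two testing strategies should differ between arms in the strategy and in what follows from it. A same-day result, with the option to wait for it, follows from decentralised testing; a later telephone call follows from centralised testing. Both belong to the contrast and are not criticised here. The list of places a positive patient is told to go does not follow from where or how the sputum was tested, and could be the same in both arms.

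Because the endpoint ends at treatment start, the referral step lies inside it. Any effect of the wording on how soon patients reach a facility, or on how soon that facility starts treatment, would be counted in the between-arm difference and could be read as an effect of the test. Section 6.4 says the study will inform government decisions on scale-up of mobile screening, so even an imprecise estimate may be used.

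**Working it through.** No figure in the protocol bears on this point. The sample-size table in section 5.9.2 concerns time to result, not time to treatment. The check is therefore a comparison of texts.

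**Step 1: the two instructions.** The standard-of-care bullet names the nearest puskesmas. The Truenat bullet names the nearest puskesmas or a hospital and adds referral to a different facility if the patient prefers. The account of current practice in section 3.2 gives no wider referral options for the comparator. On their face, the two instructions are not the same.

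**Step 2: does the later choice-of-facility sentence close the gap?** There are two readings.
- If it applies to the Truenat arm alone, as its position under that bullet suggests, the difference stands in full.
- If it is a general provision, as its wording suggests, a standard-of-care patient who asks can also be referred elsewhere. What remains is what patients are told, unprompted, when they get a positive result: Truenat positives hear of a hospital or another facility, and standard-of-care positives, on the text, do not.

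Neither reading makes the instructions identical. The second makes the difference small.

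**Step 3: where the instruction falls.** For each treated patient,

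time to treatment = (collection to result) + (result to patient informed) + (informed to arrival at facility) + (arrival to treatment start).

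The testing strategy acts directly on the first two terms. The referral instruction can act on the last two. Time to result consists of the first term alone, so it is complete before the instruction is given. Endpoints 1a to 1d (training, device performance, staff views, participant views) do not use this interval.

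**Step 4: does randomisation balance it?** No. Section 5.1 randomises screening days 1:1, and the instruction is attached to the arm. If staff follow the text, every positive in an arm gets that arm's wording, and the difference does not average out as more days are added.

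**Step 5: size and direction.** The protocol gives no treatment delay by type of facility, no split of destinations and no expected number of positives per arm. More options could shorten the delay if the patient picks a facility that is easier to reach, or lengthen it if the chosen facility is slower to start treatment. No number of days can be derived, and zero is possible.

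**The case against.** The strongest reply is that this is a difference in drafting, not in care. Several parts of it stand.

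- The protocol does not restrict standard-of-care patients to the puskesmas. A reader might infer that they are confined to it, but the text names a destination without excluding others. The follow-up interview in section 5.4.2 asks participants, with no split by arm, whether they attended a puskesmas, a private service or another one, so several destinations are expected in both arms.
- A reader might count the destinations named in each arm and treat the count as the size of the problem. It is not: if the choice-of-facility sentence is general, that option is open to both arms, and a count of destinations says nothing about delay.
- A reader might take the schedule of events, whose row reads "Referral to health facility for treatment based on Truenat MTB", as a sign that only Truenat positives are referred. Section 5.4.2 shows otherwise, since standard-of-care positives are directed to treatment too. The row is not evidence of different care.
- The standard case-finding protocols to which the section refers are not reproduced, and the Truenat-arm algorithm figure was not available for this check. Either might show a common referral pathway.
- Keeping the comparator as routinely delivered is defensible in an implementation study.
- The endpoint is secondary and acknowledged as underpowered.

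This limits the point without removing it. The instructions differ as written. Low power does not cancel a systematic difference, and the comparison will still be estimated and shown by arm. The schedule does provide for "Collection of data from health facilities and laboratory", so the route taken can be described afterwards. But the facility attended is settled after randomisation, and adjusting for it is a weaker remedy than giving both arms the same instruction. Fidelity to routine care can be kept by using the routine wording in both arms.

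**Conclusion.** The point holds in a limited form. As written, positives in the two arms are given differently worded referral instructions, and that difference lies inside the interval from sample collection to treatment initiation without being part of the testing contrast. If staff follow the text, it is a small co-intervention difference of unknown direction. If practice is already the same in both arms, it is a drafting inconsistency with no effect.

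No bias in days is claimed, and the documents would not support one. Nor do they support reading this as a threat to the powered comparison or to the feasibility findings. The conclusion rests on one assumption, that staff give the instruction set out for the arm. The change is worth making because it is cheap and removes an avoidable alternative explanation, not because a result is known to be at risk.

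**What to change.** In section 5.4.2 and the study manual, write one referral instruction for positives in both arms, with the same facility options. Either the wider Truenat wording or the routine one will do, provided it is identical in both arms. Move the choice-of-facility sentence out of the Truenat sub-list and state it once for all participants. How and when the result is given can go on differing, since that is part of what is being compared.

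The cost is a few words in two documents and a slight change to what one arm is told compared with the current text. If the wider wording is chosen, standard-of-care positives are told of somewhat more options than the text now gives them. Sample size, tests, visits and data collection stay as they are.

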5.5 Truenat arrangements

5.5.1 Truenat Storage

The devices, consumables and reagents for the Truenat assay will be stored in a secure, environmentally controlled and monitored area in accordance with the labelled storage conditions. Access to the storage site will be limited to authorised study staff.

5.5.2 Truenat Test performance

Truenat testing will be performed according to the manufacturer's instructions, as detailed within the study manual. Only authorised site staff who have been trained and assessed as competent will perform sample processing. Only sputum samples obtained for the purpose of this study from participants who have provided informed consent will be processed with Truenat.

5.5.3 Accountability

The principal investigator is responsible for trial intervention accountability and record maintenance (receipt, reconciliation, final disposition). Accountability logs will be maintained within the study to ensure appropriate handling and follow up of used, failed and unused Truenat chips. Procedures for accountability will be documented in the study manual of operating procedures.

5.6 Study screening and diagnostic algorithm

Any of these:

- Cough for 2 weeks or more
- Haemoptysis
- Suggestive CXR image, qXR indicates "TB screening advised" or interpreted as suggestive by a medical doctor
- In children 12–14 years of age: cough for 2 weeks or more, haemoptysis, weight loss, prolonged fever, or suggestive CXR image

5.7 Outcome Measures

Primary Endpoint

- 1. The operational feasibility of point-of-care Truenat, which will be assessed by:
 - a. Adequacy of Truenat training as measured by post-training assessment
 - b. Operational performance of Truenat as measured by platform failure rates and error rates
 - c. Instrument User and health service provider views regarding feasibility and acceptability of Truenat.
 - d. Screening participant views regarding acceptability of point-of-care Truenat performed within mobile active TB case finding service

Secondary endpoints

- Median time from sample collection to result for Truenat compared to centralised GeneXpert Mtb/RIF
- The median time from sample collection to treatment initiation for Truenat compared to centralised GeneXpert Mtb/RIF

5.8 Data Collection and management

5.8.1 Data management plan

Formal documentation, in the form of a data management plan will be finalised before the start of enrolment and will specify which roles in within the study team will have access to and responsibility for different levels of data. It will also specify the circumstances in which data may be accessed and the procedures for storing, backing up and accessing data.

5.8.2 Objective 1

1a Post-training test

A REDCap database will be set up to record the results of the post-training proficiency assessments conducted immediately after the training and at one month following the start of testing with Truenat. During data collection for objective 1a, data will be stored with the participant's name so that the results of the initial and follow-up proficiency assessments for each participant can be linked together. At the completion of data collection for objective 1a, names will be removed from the database and only a unique study ID and details of the participants role will be retained.

1b Failure and error rates

A REDCap database will be set up to log operational hours and platform failures:

- Date of screening
- Expected / intended duration of Truenat testing for that date
- Number of hours that platform was unavailable
- Which device failed
- Type of failure
- Remedial action required

1c User acceptability

An online REDCap survey will be set up for the survey. Each person invited to complete the survey will be provided with a unique link to prevent individuals from taking the survey more than once. Branching logic will be used to ensure that staff taking the survey are shown the appropriate sets of questions (questions relating to performing/using the assay and questions relating to the role of the assay within screening and diagnostic workflows). Survey data will be anonymous and will only record minimal detail on the role of the respondent. Responses to open-ended questions in the survey will be extracted into QSR nVIVO for qualitative coding and analysis.

1d In-depth interviews with screening participants

If the participant consents, the interview will be recorded using call recording features on the phone. As such a mobile phone designated for specific use in the study will be used for all interviews and stored in a locked filing cabinet at the Universitas Gadjah Mada when not in use. At the completion of the interview (ie on the same day that the interview is done) the audio file will be transferred to a secure Universitas Gadjah Mada file server and deleted from the portable device. Each interview will be assigned a unique ID which will be recorded alongside a minimum record of interviewee characteristics:

- Date of interview
- Interviewee gender, age

- Risk population
- Truenat result

No other identifying information about the interviewee will be associable with the interview audio, transcripts and translations.

Preference will be given to Indonesian study team members performing transcription and translation of audio recordings of the in-depth interviews with an aim to transcribe interviews within a period of 6 weeks after the interview. Third-party commercial services outside the research team may be engaged to provide transcription or translation, providing that the data handling policy of the third-party is appropriate (secure and timely) for transfer, storage and deletion of audio files, transcripts and translations. Audio recordings will remain on the UGM file server until transcription and checking are complete and the recording will then be deleted. Where transcription is performed by a third party service, the file will be transferred securely to the third party service with an agreement for the service to delete the file upon request (with the request to be made once the transcript has been completed and checked).

Transcripts will be entered into an nVIVO project along with the minimal interviewee characteristic data.

Once the last interview has been successfully transferred from the mobile phone used for interviews, a factory reset of the phone will be performed before any subsequent re-use of the phone.

5.8.3 Objectives 2 and 3

Data Collection

Data collection will be performed by trained staff delegated by the PI. Data collection on patient care will be entered into the Zero TB Initiative Yogyakarta active case finding REDCap database as per the standard of care. This database stores routine patient data for patient management as well as monitoring and evaluation and approved operational research. Each patient in the project database has a unique patient ID. For individuals enrolled in this study, a study enrolment instrument (form) will be created in the existing REDCap database that records study enrolment data (unique study ID, study date, assigned testing strategy) for patients who consent to participate in the study. The instrument and data collected using the instrument will only be accessible to study investigators such that health care workers who are not investigators do not know which patients are enrolled in the study.

LOCATE TB Research Protocol v1.1 (2022-08-25)

Source documents

The following data will be recorded directly into the electronic patient database and will be considered source data:

- Study enrolment
- Sex
- Age
- Symptoms
- Chest X-ray screen result (qXR software screening result)
- Medical history
- TB contact history
- Truenat Mtb Plus and MTB-RIF Dx; or GeneXpert MTB/Rif results
- TB diagnosis
- TB treatment
- Adverse Events

Source data for centralised GeneXpert and Truenat results will be the original reports. The results will be entered into the patient database.

Data Entry

Data entry on screening, diagnosis and treatment will be performed by the same trained staff who enter data under the current standard of care. Data will be entered during the screening and enrolment process. Follow up of the diagnosis and treatment outcomes at day 7 will occur between day 14 + / - 1 week. Study enrolment data will be entered by a member of the study team after consent is obtained.

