The phone visit or in person home visit will repeat the symptom screening questions, as well as ask about whether TB was diagnosed, how TB was diagnosed, when the participant was informed about the TB results, if and when the participant attended the health care service (Puskesmas, private or other) and if TB treatment had been commenced.

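### The protocol gives two conflicting times for ascertaining treatment start, and its named rank test has no place for positive participants who have not started

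*Protocol*

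**What the plan says.** **When treatment start is ascertained**

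- Section 2 (schedule of events) puts the item "Collection of data from health facilities and laboratory" in the column for days 7 to 21.
- Section 5.4.2 (Follow-Up Interview): "Participants will be called at a 14-day phone visit (+/- 7 days"), which is the same window. On treatment, the contact asks "if TB treatment had been commenced". It asks when the participant was told the result and when a health service was attended, but names no treatment start date.
- Section 5.8.3 (Data Entry): "Follow up of the diagnosis and treatment outcomes at day 7 will occur between day 14 + / - 1 week". One sentence holds both a day-7 outcome and the day 7–21 window.
- Table 1 (section 5.10) gives three sources for time to treatment: the active case finding database, the "Pusksemas Database" and a "Week-1 telephone call".

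**Who is counted, and how they are compared**

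- Table 1 defines the population for this endpoint as participants with an initial positive molecular result. That includes people who have not started treatment.
- Section 5.10.2 concedes that power is insufficient, then says that "the median time from sample collection to treatment initiation will be calculated for the two groups". Kaplan-Meier curves by arm are to describe the time-to-event data, with details left to the SAP.
- The next paragraph plans interquartile ranges and box plots for every median, "with differences in medians compared using the Wilcoxon signed rank test", with Mann-Whitney added in brackets. I read this as the two-sample rank test.

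**The concern.** An analyst working from this text cannot tell whether the endpoint is status at day 7, status on whichever day the call was made, or status by day 21. The SAP can choose among these only if the data were collected to match, so this has to be settled in the protocol.

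The named test adds to the difficulty. An ordinary rank test needs a value for each person, and someone who has not started has none. If such people are left out, the comparison is made among starters seen within the window. Late starters are cut off, and there should be more of them in the arm whose result arrives later. People who never start contribute to neither median, although sections 3.2 and 6.4 name less loss to follow-up as an expected benefit of decentralised testing. An avoidable pull towards no difference is unwelcome for an endpoint already described as underpowered.

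**Working it through.** **1. The times side by side.**

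| Place | Time |
|---|---|
| Section 2, schedule of events | day 7–21 |
| Section 5.4.2, follow-up call | day 14 ± 7, i.e. day 7–21 |
| Section 5.8.3, Data Entry | outcomes at day 7, followed up at day 14 ± 7 |
| Table 1, telephone source | week 1 |

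These amount to two times: week 1 (day 7) and a window of day 7–21. Across that window the longest observation is 21/7 = 3 times the shortest.

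**2. The plan's own figures.** None concerns time to treatment. The only powered comparison is time to result (section 5.9.2). Its table reproduces under a log-normal model:

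- σ² = ln[(1 + √(1 + 4(sd/median)²))/2] for each arm
- n = (σ₁² + σ₂²)(1.960 + 0.842)² / [ln(m₁/m₂)]²

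For medians 3 and 2 with sd 21: (2.017 + 2.399) × 7.849 / 0.1644 = 210.8, so 211. The other rows give 28.1, 33.1 and 175.0, so 29, 34 and 175. All four match. The protocol does not name the distribution, so the log-normal is inferred from this match.

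**3. A proxy for direction.** Under that model, the share of results arriving after day t is 1 − Φ(ln(t/median)/σ). Ranges run from sd 14 to sd 21.

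| | after day 7 | after day 21 |
|---|---|---|
| Standard of care, median 3 | 25–28% | 6–9% |
| Truenat, median 2 | 19–21% | 5–6% |
| Truenat, median 1 | 12–13% | 3–4% |

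This describes results among everyone tested, not treatment among positives. It supports the direction only: treatment based on a positive result cannot precede that result.

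**4. Illustration for time to treatment.** Every input here is assumed: log-normal times, log-SD s of 0.8 to 1.0, medians m of 3 days (Truenat) and 5 days (standard of care), and a fraction p = 10% never starting in each arm. With cut-off T and F = Φ(ln(T/m)/s):

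- share with an observed start = (1 − p)F
- median among observed starters = m·exp[s·Φ⁻¹(F/2)]
- median with all positives kept = m·exp[s·Φ⁻¹(0.5/(1 − p))]

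Example with s = 0.8 and T = 7:

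- Standard of care: F = 0.663, share 0.597, starters' median 3.53.
- Truenat: F = 0.855, share 0.770, starters' median 2.59.
- Difference among starters: 0.94 days.
- Difference with all kept: 5.59 − 3.35 = 2.24 days.

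Over s = 0.8 to 1.0:

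| Cut-off | Observed start, Truenat | Observed start, standard of care | Difference, starters only | Difference, all kept |
|---|---|---|---|---|
| day 7 | 72–77% | 57–60% | 0.8–0.9 d | 2.2–2.3 d |
| day 14 | 84–88% | 76–81% | 1.4–1.6 d | 2.2–2.3 d |
| day 21 | 88–89% | 83–87% | 1.6–1.8 d | 2.2–2.3 d |

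The gap in capture between arms is 15–17 percentage points at day 7 and about 3–4 at day 21. Other scenarios used medians 5/7 and 3/7, and 20% never starting under standard of care. Across all of them the starters-only difference was 0.5–1.5 days at day 7 and 1.4–3.5 at day 21, against 2.2–6.2 with all positives kept.

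**The case against.** The strongest reply is that the protocol nowhere excludes non-starters. It plans Kaplan-Meier curves, which keep them as censored, cope with unequal follow-up and can yield the medians themselves, and it leaves details to an SAP that is not at hand. This stands against any statement that late and never starters will drop out. A reader might infer that from the rank test, but it is a possible consequence and not a stated rule.

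Second, the call is not the only source. The two databases in Table 1 and the facility data collection in the schedule can supply a start date missed at an early call. This also stands, but it does not remove the conflict: facility data collection falls in the same floating window, with no common cut-off.

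Third, section 5.10.2 attaches its test of significance to time to result, and for treatment says only that medians are calculated. The scope of the Wilcoxon clause is arguable. Since it follows directly on a statement about all medians, the natural reading includes treatment time. If that is not intended, the protocol should say so.

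Fourth, a reader might take the 25–28% of standard-of-care results after day 7 to mean that at least a quarter of treatment starts would be missed. The documents do not support that. The figure concerns results under an inferred distribution, and the loss would need a hard day-7 cut-off with no use of facility records.

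**Conclusion.** The point holds in a limited form. The protocol conflicts on when treatment start is ascertained, and the comparison it names does not fit a population that includes people without a start date. Both are stated in the protocol itself and are not left to the SAP.

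The bias is conditional. It arises only if the comparison is confined to starters, and it then probably runs towards no difference. Its size depends on the limit chosen: on assumed inputs, a true difference of 2.2–2.3 days loses more than half its size at day 7 and roughly a fifth to a quarter at day 21. Section 5.4.2 expects standard-of-care results within 1–3 days, so the arms may differ by little and the day-21 effect may be small. No figure in the protocol fixes these inputs.

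This is a secondary, admittedly underpowered endpoint. The correction is worth making because it is cheap, and because data collected at unequal times cannot be repaired at analysis.

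**What to change.** - **Timing.** Reconcile Table 1 and section 5.8.3 with the existing window by removing the week-1 and day-7 references. State one ascertainment limit for every participant: treatment start up to day 21, the end of that window.
- **Data.** Record the treatment start date from the puskesmas and active case finding databases for all participants with an initial positive result. Use the call as a supplement, and add the start date to its questions.
- **Analysis set.** Keep everyone with an initial positive result, and censor those not started at day 21. Where status is known only from an earlier call, for example because care was sought elsewhere, censor at that date.
- **Comparison.** For this endpoint, replace the rank test with Kaplan-Meier medians or the proportion started by day 21. Add a log-rank or Cox comparison that allows for randomisation by screening day (section 5.1).

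The cost is wording in Table 1 and sections 5.4.2, 5.8.3 and 5.10.2, one register look-up at day 21 from sources already listed, and slightly more analysis.
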